### Design

This is a parallel-group, double-blind, placebo (PBO)-controlled, randomized Phase 2 pilot study using adjunctive dehydroxyepiandrosterone [DHEA (400 mg)] will be evaluated to establish Proof of Concept (POC) for this agent in OEF/OIF/OND Veterans with PTSD.

Aim 1. To determine the effects of an acute oral administration of adjunctive DHEA (400 mg) on neuroimaging measures of functional connectivity. We will conduct a parallel-group, double-blind, placebo (PBO)-controlled, randomized Phase 2 pilot study with one-time oral DHEA 400 mg in target engagement. To establish POC, we seek to determine if DHEA is superior to PBO in target engagement of neural circuits related to fear-anxiety-emotion regulation using the shifted-attention emotion appraisal (SEAT) paradigm (see below). Following a two-week placebo lead-in period (all participants), subjects will be randomized to receive a one-time oral dose of adjunctive DHEA (400mg) or PBO. Neuroimaging will occur 2 hours following drug administration for peak level effects on target engagement of fear-anxiety emotion circuit connectivity, as previously conducted by Sripada, [name], [name] et al.).

Primary Outcome Measure The primary outcome measure will be functional connectivity between amygdala-hippocampus assessed using fMRI based SEAT Paradigm as a target engagement endpoint. The fMRI based SEAT Paradigm has been previously validated to an acute administration of DHEA (400 mg) in healthy volunteers by members of my career development team, Drs. [name] and [name] (Sripada et al., 2013).

Aim 2. To evaluate a sustained 6-week adjunctive DHEA treatment compared to PBO on PTSD symptoms severity (CAPS-5), co-occurring depression (BDI), and other secondary outcome measures such as resilience (CD-RISC). Following randomization to acute DHEA administration or PBO the subject will continue to receive study drug for 6 weeks (for DHEA, fixed escalating doses: 100 mg per day in divided doses x 1 week, followed by 200 mg per day in divided doses x 1 week, followed by 400 mg per day in divided doses x 4 weeks).

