For fMRI analysis we will use FSL supplemented by BIRN tools for signal averaging, ROI analysis, and visualization of time series waveforms (Smith SM 2004). We use FreeSurfer for surface reconstruction and automatic segmentation. FMRIB Software Library (FSL) preprocessing will be used for motion correction, slice time correction, temporal and spatial filtering, and co-registration with the individual subject's high resolution anatomical image. A first level analysis will be performed on each run separately using a standard GLM approach with regressors determined by the task timing convolved with a delayed canonical hemodynamic response. The first level analyses from a subject will then combined in a fixed effects second level analysis. These second level analyses are then combined into between group third level analyses using a mixed effects model. The functional MRI data will be analyzed by comparing whole brain voxelwise neural activity (BOLD) associated with cognitive processing between pre- and post-treatment, between active and placebo arms, between-face types (e.g. angry, fearful, neutral), and between-task conditions (e.g. gender, indoor/outdoor, like/dislike), which is neurosteroid relevant (Sripada et al 2013a, Sripada et al 2013b). [name] was the

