## PROTOCOL

Neurosteroids as Novel Therapeutic Agents for PTSD in OEF/OIF/OND Veterans  
PI: [name], PhD

senior author on these pivotal trials and is a collaborator (please see accompanying letter) along with [name] who was a co-investigator and is the primary mentor for the CDA. Subsequent testing with functionally defined ROIs will be used to make statistical inferences about treatment response and to identify correlations with cognitive changes, CAPS-5 scores, and neurosteroid levels. In addition, we propose to study the correlation between PTSD symptom severity and disruption in fear systems interrogated by the task paradigms. This will be probed further by examining correlation between the hypothesized clinical behaviors and fear system activation during the associated task (e.g., severity of hypervigilance symptoms and activation. Correction for the family-wise error rate will be based upon the Gaussian random field (GRF) theory that is implemented in FSL (Worsley et al., 1996).

Primary outcome analyses will be based on maps of activation, reaction time, and on-line accuracy judgments via a 2 (drug type: DHEA or Placebo)  $\times$  3 (face type: angry, fearful, neutral)  $\times$  3 (condition: male/female, inside/outside, like/dislike) repeated-measures ANOVA for main effects and interactions. Follow-up effect analyses will be performed with two-tailed *t*-tests and significance threshold at 0.05 with correction for multiple comparisons. Z-score images from the individual activation maps will be entered in second-level random-effects analyses using SPM8 and corrected for multiple comparisons,  $p<0.05$ . Activation threshold and cluster size will be determined using AlphaSim (Ward, 2000) to correspond to a false-positive rate of  $p<0.05$ , corrected for multiple comparisons within ROIs. Voxel coordinates that will be reported will correspond to standardized MNI space. The time series from significant clusters within regions of group difference will be used in a psychophysiological interaction (PPI) analysis. Deconvolved time series in the anatomical right amygdala will be extracted for each subject and represent the first regressor in the PPI analysis (physiological variable). The experimental condition is the second regressor (emotion processing; psychological variable). The regressor of interest will be the interaction between the time series of the seed region and the experimental condition.

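### Entering first-level Z-score images in the group analysis makes the activation comparison a test of signal-to-noise, so a drug effect on within-subject noise can pass for an activation effect

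*Combined protocol and SAP*

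**What the plan says.** The relevant text is in Data Analysis and Statistical Considerations.

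- **The primary outcome paragraph** opens with "Primary outcome analyses will be based on maps of activation, reaction time, and on-line accuracy judgments", analysed in a drug by face type by condition repeated-measures ANOVA. Follow-up tests are two-tailed, with "significance threshold at 0.05 with correction for multiple comparisons". It then states the group-level input: "Z-score images from the individual activation maps will be entered in second-level random-effects analyses using SPM8 and corrected for multiple comparisons". Cluster thresholds come from AlphaSim within regions of interest.
- **The fMRI paragraph before it** describes a different route, in FSL. It begins "A first level analysis will be performed on each run separately using a standard GLM approach", combines runs by fixed effects, and continues: "These second level analyses are then combined into between group third level analyses using a mixed effects model". Family-wise error is controlled there by Gaussian random field (GRF) theory. The paragraph does not name the image passed from level to level.
- **The link to connectivity** follows the SPM8 step: "The time series from significant clusters within regions of group difference will be used in a psychophysiological interaction (PPI) analysis". The seed time series is taken from the anatomical right amygdala. The image entered at group level for the psychophysiological interaction (PPI) is not stated.
- **The Design section** declares the outcome itself: "The primary outcome measure will be functional connectivity between amygdala-hippocampus assessed using fMRI based SEAT Paradigm".

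The plan does not say which of the two pipelines governs, and it gives no reason for using Z images.

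**The concern.** A first-level Z image is, up to a monotone conversion, the effect estimate divided by its SE. That SE reflects motion, physiological noise and residual variance in the one participant. A random-effects test on Z therefore asks whether the arms differ in the ratio of response to noise. The scientific question is whether they differ in the response.

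Two consequences follow. If the drug lowers or raises within-subject noise, Z shifts in that arm wherever mean activation is not zero, even when the response is unchanged. If noise merely varies between participants, that variation is carried into Z and can blur a true difference. The plan lists motion correction as preprocessing, but no comparison of motion or first-level residual variance between arms, so such a shift could go unnoticed.

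**Working it through.** **Sample size.** The Design section randomises 40 and assumes 20% drop-out: 40 × 0.80 = 32, or 16 per arm. The exploratory aim's 80% imaging uptake gives the same 32. (The statistics section attaches a 10% drop-out to the same 32; 40 × 0.90 = 36, so only 20% reproduces it.) No power, effect size, SD or noise figure is given for the imaging outcome. Every variance below is therefore an assumption.

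**Why noise matters only when mean activation is not zero.** Let b be a participant's contrast estimate with mean μ, and Z = b/SE. If the error in b averages zero whatever the SE, then E[Z] = μ × E[1/SE]. Multiplying the SE in the drug arm by r changes that arm's mean Z to μ × E[1/SE] / r. With μ = 0 nothing moves. With r = 1 the arms stay equal.

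Numerical check, with lognormal SE of median 0.7 and log-scale spread 0.3:
- E[1/SE] = exp(0.3²/2)/0.7 = 1.046/0.7 = 1.494.
- With μ = 1, mean Z is 1.49 on placebo.
- With r = 0.8, mean Z is 1.494/0.8 = 1.87 on drug, with no true difference. Simulation gave 1.50 and 1.87.

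**False positives.** Assumptions: 16 per arm, between-subject SD 0.87, mean SE 0.5, coefficient of variation (CV) of the SE 30%, no true difference, two-sided two-sample t-test at 0.05 at one uncorrected location, 20,000 simulated trials. The total SD is √(0.87² + 0.5²) = √1.0069 ≈ 1.00, so μ is roughly in SD units. Simulation error near 5% is √(0.05 × 0.95/20,000) ≈ 0.15 percentage points.

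| Mean activation | Z images, noise 20% lower on drug | Z images, noise 33% lower on drug |
|---|---|---|
| 0 | 5.0% | 5.1% |
| 0.25 | 4.8% | 6.3% |
| 0.5 | 6.2% | 8.0% |
| 1 | 8.7% | 17.1% |

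Noise 10% lower at mean 1 gives 5.5%.

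A second set (between-subject SD 0.7, median SE 0.7, 40,000 trials) gave 9.2% at mean 1 with noise 20% lower and 16.2% with noise 30% lower. Contrast estimates stayed at 4.8% to 5.0% in every null setting, and Z did too when the drug left noise unchanged. The range is not a ceiling: at mean 2 this set gave 18.4% and 40.3%.

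**Power, equal noise in both arms, true difference 1.** Between-subject SD 0.87 and mean SE 0.5 for the CV 30% and 50% rows; for the others, total SD about 1 with the split described.

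| Setting | Z images | Contrast estimates |
|---|---|---|
| Same SE for everyone | 0.78 | 0.78 |
| CV 30%, control mean 0 | 0.765 | 0.776 |
| CV 30%, control mean 0.5 | 0.735 | 0.769 |
| CV 30%, control mean 1 | 0.69 | 0.77 |
| CV 50%, control mean 1 | 0.57 | 0.75 |
| Within-subject noise dominates, SE spread 0.4, control mean 1 | 0.66 | 0.68 |
| Within-subject noise dominates, SE spread 0.4, control mean 0 | 0.78 | 0.68 |

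Power can fall, stay level or rise.

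**Power when the drug also changes noise** (second set, control mean 1, true difference 1): noise 20% lower on drug gives 0.93 for Z against 0.79 for contrasts; noise 25% higher gives 0.36 against 0.69.

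**The case against.** The case against has several parts, and much of it stands.

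- **The trigger is not documented.** Nothing in the documents says that DHEA alters motion or physiological noise, and motion correction is planned. A shift is conceivable: the rationale is an anxiolytic action, and the risk sections note that the scanner can provoke claustrophobic feelings, so calmer participants might move less. That is inference, not evidence.
- **The mean activation is unknown.** The visible inflation needs a mean of about one SD. The ANOVA's face and condition terms are differences between conditions, whose mean could be much smaller.
- **The simulated test is not the planned one.** It is a single uncorrected comparison; the plan uses a 2 × 3 × 3 ANOVA with cluster correction. The rates illustrate the mechanism and are not the plan's error rates.
- **A reader might infer that Z images dilute true effects as a rule.** The power table does not support that.
- **A reader might infer that the declared primary outcome is biased.** The documents do not show it. The Z sentence concerns activation maps, the amygdala seed is anatomical, and the group-level PPI image is not stated. The remaining route is the clusters of group difference passed to the PPI, and the plan does not explain how they enter a model with an anatomical seed.
- **A reader might infer two contradictory inputs.** The FSL paragraph names no input, so what is shown is two unranked pipelines. If the FSL route governed and carried contrast estimates, the Z sentence would be moot.

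What survives is that the plan states a specific input for the analysis it labels primary, gives no reason for it, and that input does not measure response size.

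**Conclusion.** The concern holds in a conditional form. On the natural reading of an undefined term, the activation comparison tests signal-to-noise. It can give a false difference only where the drug changes within-subject noise and mean activation is not zero; if either is absent, the error rate stays near 5%.

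Under the main assumed setting, with mean activation between 0 and 1, false positives range from 5% to about 9% (noise 20% lower on drug) or 17% (33% lower). With equal noise in both arms, the result ranges from no loss of power to about 0.57 against 0.75, with a gain for Z possible when within-subject noise dominates and control activation is near zero. The documents cannot place the trial within these ranges.

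This is a choice that should be corrected because the better input is readily available. It is not a demonstrated error in the connectivity endpoint.

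**What to change.** In the primary outcome paragraph of Data Analysis and Statistical Considerations:

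1. Replace the Z-score images with first-level contrast (parameter-estimate) images, carrying their variances forward where the mixed-effects model of the fMRI paragraph is used.
2. State which single pipeline governs the primary imaging test: FSL mixed effects with GRF correction, or SPM8 with AlphaSim.
3. State that contrast estimates of the PPI interaction term are entered at group level.
4. Keep Z maps for display only.
5. Report motion and first-level residual variance by arm.

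The cost is a change of wording, ideally before unblinding. Contrast images and residual variances are standard first-level output, so no new data, scans or participants are needed.

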## PROTOCOL

Neurosteroids as Novel Therapeutic Agents for PTSD in OEF/OIF/OND Veterans  
PI: [name], PhD

Analyses will be based on a modified intent-to-treat methodology; all participants who reached one or more study visits post-randomization will be included in the statistical analysis plan. We will randomize a total of 40 participants; it is estimated that at least 32 participants will receive at least one study visit post-randomization and will be included in the statistical analyses (10% drop out rate assumed). Analyses thus utilize an n=32 for power calculations in the proposed modified intent-to-treat analysis. We will make significant efforts to obtain final interviews with drop-out subjects to determine if drop-out is in fact treatment-related as opposed to MAR. In instances where contact is not possible or assumptions of MAR are confirmed by interview, missing data will be augmented where assumptions that the pattern of 'missingness' are ignorable (e.g., MAR - Schafer, 1997) hold using multiple imputation procedures including maximum likelihood (e.g., PROC MIXED: see above) or, in instances where missing data include independent measures, multiple imputation (e.g., SAS: PROC MI; R: MICE). Subsequent sensitivity analyses comparing results based on various methodologies are of course essential in determining how robust results are to missing data.

Change in total DSM5-defined PTSD symptoms from pre- to post- treatment, as assessed by the CAPS-5, the gold standard method for assessing PTSD symptoms in pharmacological treatment trials; measurements will be gathered at two-week intervals beginning at baseline and continuing through Week 8. Measures of pre-post treatment differences at the four study intervals will be regressed on a dichotomous proxy measure denoting treatment status coded positive for subjects randomized to the DHEA condition. In addition to the treatment proxy, all models will include covariates for measurement interval (time), and an interaction term crossing the treatment proxy with time. Test of the secondary hypothesis will be based on a 1 df test of the contrast of difference between drug and placebo at the final time point (SAS: LSMESTIMATE statement). Specifically at Week 8, H0: LSMEdhea  $\geq$  LSMEplacebo versus Ha: LSMEdhea  $<$  LSMEplacebo. We hypothesize rejection of a null hypothesis positing that difference in PTSD symptoms from baseline will be equivalent or greater among subjects randomized to DHEA at the final time point in lieu of an alternative hypothesis positing a reduction in PTSD symptoms in the DHEA cohort relative to placebo.

Measures of serum levels of three neurosteroids: DHEA, DHEAS, and androsterone will also be analyzed. As above, the outcome measure will be the change in steroid level from baseline (i.e., following 2 week placebo lead in) to Week 8 with measurements at two-week intervals. Models will be estimated as described above with tests of the primary hypothesis based on a 1 df test of the estimated contrast of the difference between drug and placebo at the final time point. In all cases, the following hypothesis will be tested: H0: LSMEdhea  $\leq$  LSMEplacebo versus Ha: LSMEdhea  $>$  LSMEplacebo. Results for tests of Aim 2 will be adjusted for multiple comparisons using the method of Hochberg (1998).

As secondary test of the hypothesized association between change in PTSD status and change in neurosteroid levels, Week 8 changes CAPS-5 scores will be regressed on Week 8 change in neurosteroid levels. Models will include, as above, covariates for age, gender, smoking status, depression, TBI status, and a measure of the baseline level of the tested neurosteroid. Based

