### Exploratory Outcome Measures

The exploratory outcome measures will include: STI (myelin integrity); fMRI measures (amygdala and hippocampal connectivity); serum neurosteroid levels (DHEA; DHEAS; androsterone); PTSD symptom severity (CAPS-5); and other rating scale measures of co-occurring symptoms.

*Experimental Design:* The proposed design is a parallel-group, double-blind, PBO-controlled, randomized Phase 2 pilot study of adjunctive DHEA vs. PBO to determine target engagement of fear-anxiety-emotional circuit regulation and potential efficacy of DHEA in 40 OEF/OIF/OND Veterans with PTSD. Subjects will be randomized to receive a one-time oral dose of DHEA (400mg) or PBO and sustained administration of the study drug for 6 weeks. There will be a 2 week placebo lead-in period [all participants], followed by subjects continuing in the randomization block of DHEA or placebo for 6 weeks following acute administration. 40 subjects will be randomly assigned to one of two groups; assuming approximately a 20% drop-out rate, we anticipate that 32 participants will have at least one visit post-randomization and will be included in the statistical analysis plan (approximately 16 participants per group); a modified intent-to-treat approach will be utilized. The research pharmacist at the Durham VA will be responsible for randomization of participants in this study; a randomized block design will be utilized (4 participants).

*Shifted-Attention Emotion Appraisal (SEAT) Paradigm:* In order to investigate the brain basis of fear-anxiety emotional response and regulation, [name] laboratory has developed an emotion appraisal task (Klumpp et al, 2011; Sripada et al., 2013), modifying the task of Anderson et al (2003), and collaborating with [name] to evaluate the impact DHEA in healthy volunteers. My mentoring and collaborative team has thus demonstrated that the SEAT paradigm is an effective probe of neurosteroid regulatory effects (Sripada et al, 2013). The SEAT task uses compound stimuli that include emotional faces and neutral scenes. Stimuli include pictures of faces in front of buildings, as well as 20 pictures of faces or buildings alone. The face pictures represent neutral, angry, or fearful expressions, and the buildings are of indoor or outdoor portraits.

Participants are asked to respond to three different questions, in three different conditions: (1) 'Gender': whether the face is male or female; (2) 'Inside/Outside':

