### Data Analysis and Statistical Considerations

The analysis plan is organized around the study's hypotheses using a variety of statistical techniques. Univariate summary statistics, including means, medians, rates, proportions, and variances, will be calculated as appropriate for all variables. In addition to statistics, outcome measures will be examined graphically to assist in determining distributional form as a precursor to model selection. Preliminary bivariate analyses by treatment condition will use standard Chi-square procedures for categorical outcomes; continuous outcomes meeting distribution requirements will be tested using Student's t-test, whereas data not meeting distributional requirements will be analyzed by nonparametric (e.g., Kruskal-Wallis) procedures. Differences between covariates will be tested at baseline to assess randomization. Putative covariates with significant asymmetry between groups will be considered for inclusion in subsequent modeling and testing (However, see Miller & Chapman, 2001). Inference for all analyses will be evaluated relative to  $p=0.05$  within a given hypothesis.

Analysis of primary outcomes in the Shifted-Attention Emotion Appraisal (SEAT) Paradigm will present compound stimuli that include both emotional faces (e.g. sad, happy, angry) and neutral scenes (Sripada et al 2014). In three different conditions, participants will be asked to respond to three different questions: (1) 'Gender': Whether the face in the foreground is male or female; (2) 'Inside/Outside': Whether the scene in the background is indoors or outdoors; or (3) 'Like/Dislike': Whether the face in the foreground is liked or disliked. This allows multiple components of cognition to be probed including (1) implicit emotional processing, (2) attentional modulation, and (3) cognitive modulation of emotion. Item-specific memory will be tested first using yes/no recognition judgments. The conjunctive memory test will require participants to make "match" (previously viewed faces and buildings presented in a combinations seen during encoding) or "mismatch" (items in combinations not previously seen together) judgments.

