## PROTOCOL

### Neurosteroids as Novel Therapeutic Agents for PTSD in OEF/OIF/OND Veterans

PI: [name], PhD

on anticipated collinearities between the dichotomous randomization proxy and change, models will initially be estimated without the former. A significant inverse association between change in steroid levels and change in CAPS-5 scores would support the hypothesized efficacy of DHEA as an adjunctive therapy in treating PTSD. As above, results would be corrected for multiple comparisons.

Tests of secondary measures will be conducted as described above. Thus, proposed measures will be regressed as change from baseline scores on a model controlling for the baseline level of the tested outcome measure, the dichotomous randomization proxy, and an interaction term crossing the latter with time. Tests will again be based on a 1 df test of the estimated contrast (LSME: see above) of the difference between drug and placebo at the final time point. Expectations are that change in adverse outcome measures will be significantly mitigated in the DHEA intervention arm; measures associated with salubrious outcomes will be, conversely, improved. All results will be adjusted for multiple comparisons.

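### The CAPS-5 and neurosteroid change models list no baseline value of the outcome, although the model for the other secondary measures does; this costs precision at about 16 per arm

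*Combined protocol and SAP*

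**What the plan says.** All of this is in Data Analysis and Statistical Considerations.

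- **CAPS-5.** Change from baseline is regressed on a two-level treatment indicator, and "all models will include covariates for measurement interval (time), and an interaction term crossing the treatment proxy with time". The test is a 1-df least-squares-means contrast at Week 8. It is written one-sided, with an alternative "positing a reduction in PTSD symptoms in the DHEA cohort relative to placebo".
- **Neurosteroids.** The change models for DHEA, DHEAS and androsterone refer back to the CAPS-5 model, so they carry the same terms.
- **Steroid association.** The regression of Week 8 CAPS-5 change on Week 8 steroid change lists several covariates, including the baseline steroid level, but not baseline CAPS-5.
- **Other secondary measures.** The text refers back to the earlier model and then restates it: "proposed measures will be regressed as change from baseline scores on a model controlling for the baseline level of the tested outcome measure", followed by "the dichotomous randomization proxy, and an interaction term crossing the latter with time". Baseline is now named. The time main effect is not.

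On size and error rate: "Analyses thus utilize an n=32 for power calculations in the proposed modified intent-to-treat analysis", and "Inference for all analyses will be evaluated relative to $p=0.05$ within a given hypothesis".

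**The concern.** The two term lists are presented as the same model but differ. The main clinical scale has the list without baseline, and the other scales have the list with it.

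A change score subtracts the whole baseline value. If the slope of Week 8 on baseline is below 1, this over-corrects: it adds noise, and part of any chance baseline difference between arms passes into the contrast. With about 16 per arm, such differences are not rare.

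The mismatch also leaves an analyst two defensible CAPS-5 models, with and without baseline. They would give different p-values, and the documents do not settle which one applies.

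**Working it through.** **Inputs from the documents.** Forty are randomised and 32 analysed, about 16 per arm (Experimental Design, under Exploratory Outcome Measures). Alpha is 0.05 and the CAPS-5 hypothesis is one-sided (statistical section). Entry requires CAPS-5 of at least 33 (Inclusion Criteria).

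**Inputs assumed.** The documents give no SD, effect size or baseline-to-Week 8 correlation rho. I take rho from 0.3 to 0.8 and a true difference of 0.8 of the Week 8 score SD.

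**The plan's own figure.** 40 × (1 − 0.20) = 32, which reproduces the stated number. The 10% drop-out quoted beside the same 32 in the statistical section would give 36. I use 32. No power figure is stated, so there is none to reproduce.

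**Step 1: equal SDs at baseline and Week 8 (SD = 1).**
- Variance of a change score: 2(1 − rho).
- Variance after adjusting for baseline: 1 − rho².
- Ratio, adjusted to unadjusted: (1 + rho)/2.
- Participants the unadjusted model needs to match 32 adjusted ones: 32 × 2/(1 + rho).

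Power is from the noncentral t, one-sided 0.05, with noncentrality 0.8/(SD × √(2/16)) on 30 df unadjusted and 29 df adjusted.

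| rho | Change variance | Adjusted variance | Ratio | Power unadjusted | Power adjusted | Equivalent N |
|---|---|---|---|---|---|---|
| 0.3 | 1.40 | 0.91 | 0.65 | 0.59 | 0.75 | 49 |
| 0.5 | 1.00 | 0.75 | 0.75 | 0.71 | 0.82 | 43 |
| 0.7 | 0.60 | 0.51 | 0.85 | 0.89 | 0.93 | 38 |
| 0.8 | 0.40 | 0.36 | 0.90 | 0.97 | 0.98 | 36 |

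Multiplying the adjusted variance by 1 + 1/28, to allow for estimating the baseline slope, lowers the adjusted powers to 0.74, 0.81, 0.92 and 0.98.

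**Step 2: chance imbalance.** The standard error of the baseline difference between arms is √(2/16) = 0.35 SD, so a difference larger than this is expected in about one trial in three. With equal SDs the change score leaves (1 − rho) of it in the contrast. For an imbalance of 0.35 SD that is 0.25 SD at rho 0.3, 0.18 at 0.5 and 0.11 at 0.7. Averaged over randomisations it is zero.

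**Step 3: narrower baseline.** Let the baseline SD be k times the Week 8 SD. The ratio becomes (1 − rho²)/(1 + k² − 2·k·rho). The entry threshold could plausibly make k less than 1.

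| k | rho 0.3 | rho 0.5 | rho 0.7 |
|---|---|---|---|
| 0.6 | 0.91 | 0.99 | 0.98 |
| 0.8 | 0.78 | 0.89 | 0.98 |

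The ratio reaches 1.00 when rho = k, because the slope rho/k is then 1 and the change score already makes the right correction.

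**Step 4: the unnamed time term.** I took a common improvement in both arms with no drug effect (assumed mean changes of −3, −6, −8 and −9 at Weeks 2 to 8) and fitted treatment and treatment by time without a time main effect.
- Treatment and time as class factors: the design keeps rank 8, the same as with time included, and the Week 8 contrast is 0.0.
- Treatment as a numeric 0/1 variable: the placebo mean is forced flat, and the contrast is −2.5 to −3.0, a false benefit.

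**The case against.** Three points can be made for the plan.

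**The missing baseline may be only an incomplete list.** Secondary Outcome Measures names CAPS-5 first, so the later sentence that adjusts secondary measures for baseline could be read to cover it. The steroid association paragraph also speaks as if its covariates had been listed earlier. This stands as a possible reading. But CAPS-5 has its own model paragraph and its own hypothesis test, and the steroid change models refer back to that paragraph. The text does not settle it, which is why it needs stating.

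**The gain may be small, and the outcome is secondary.** This stands. The figures in Step 1 need equal SDs. Step 3 shows that a narrowed baseline can remove nearly all of the gain, and at rho 0.8 there is little to win in any case. The plan also allows covariates that differ significantly between arms to be considered for later models, though choosing adjustment after a significance test is a poor substitute for naming baseline in advance. The primary outcome is fMRI connectivity, and the trial is a pilot.

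**The time term is not dropped.** A reader might infer that the other secondary measures are analysed without time, so that improvement shared by both arms is credited to DHEA. The documents do not support this. The CAPS-5 paragraph says that all models include time, and the later paragraph refers back to it. A least-squares-means contrast by arm implies class factors, for which treatment by time already spans time (Step 4). A false benefit would need two things together: a literal omission of time, and treatment entered as a numeric 0/1 variable. The plan's description of treatment as a dichotomous proxy leaves the coding open, so the list should be completed, but that is a wording repair.

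**Conclusion.** The point holds as a loss of precision and an inconsistency of specification. The CAPS-5 and neurosteroid change models do not list the outcome's baseline value, while the model for the other secondary measures does.

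With equal SDs and rho from 0.3 to 0.8, the unadjusted standard error is 24% to 5% larger than the adjusted one. The power lost at a 0.8 SD difference runs from about 16 points down to about 1. With a baseline SD of 0.6 to 0.8 of the Week 8 SD, the variance ratio is about 0.78 to 1.00. All of these rest on assumed values of rho, the SD ratio and the effect size.

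It is not a bias in expectation, because randomisation protects the contrast on average. The change is worth making because it is nearly free, and because the CAPS-5 model should be fixed before unblinding.

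**What to change.** State one model for CAPS-5, every other scale and each neurosteroid:

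- change from the pre-dose baseline, regressed on that outcome's own baseline value, treatment, categorical time and treatment by time;
- treatment and time both as class factors;
- the existing 1-df contrast at Week 8.

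Name the visit that serves as baseline. The steroid paragraph places it after the two-week placebo lead-in, while the general description lists Week 2 among the change-score time points. Name the time main effect in the paragraph on the other secondary measures, so that the two lists agree. Add baseline CAPS-5 to the regression of Week 8 CAPS-5 change on steroid change.

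The cost is a few sentences and one degree of freedom for baseline in each model. A baseline-by-time interaction would cost more and is optional. No new data are needed: the Schedule of Events already has CAPS-5, the other assessments and a blood draw at both Week 0 and Week 2.
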